### **13 Programming Considerations, Listing of Tables, Figures & Format, Software detail**

All tables, data listings, figures (TLFs), and statistical analyses will be generated using SAS® for Windows, Release 9.4 (SAS® Institute Inc., Cary, NC, USA) or any other validated statistical software. One SAS program will be used to create several outputs / a separate SAS program will be created for each output. Output files will be delivered in Word / pdf format.

For few assessments (weight, physical examination, vital signs haematology, biochemistry Chest X Ray/CT scan), screening assessments will be considered as baseline assessment (as day 1).

Missing data:

All attempts will be made to collect all data per protocol. Any data point that appears to be erroneous or inexplicable based on clinical judgment will be investigated as a possible outlier. If data points are identified as outliers, sensitivity analyses may be performed to examine the impact of including or excluding the outliers. Subjects who meet fatal outcome during the observing period up to 30 days will be an event. Subjects lost to follow up or withdraw consent during the observing period, will be censored at last assessment. Patient data will be censored at the time of their last observed assessment in case of lost to follow up, withdrawal consent or after 30 days of enrolment.

Following Rules may be applied for the derivation of efficacy endpoints

- Patients who discharged from hospital (with improvement, Off O2), the status at discharge will be carried forward.
- Patients who lost to follow up will be considered as Non evaluable (NE)
- Patients who worsen or met fatal outcome, status at event will be carried forward.

Note: Telephonic improvement of weaning of O2 will be considered as improved.

These rules will be applied to analyse following endpoint:

Proportion of patients with deterioration of lung function as measured by:

- Stable SpO2 without increasing FiO2
- Stable PaO2 without increasing FiO2

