8.1 Schedule of Study Visits and Procedures

Visit	S1	W1	W2	W3	W4	End of Study
Weeks	-2 to 0	0	1	2	3	4 th week
Days	-14	1 [^]	8 [^]	15 [^]	22 [^]	30 [#]
Event						
Informed Consent	X					
Medical History	X					
Inclusion/Exclusion Criteria ^a	X					
Weight	X	X	X	X	X	X
Physical Examination, Vital signs ^{\$}	X	X	X	X	X	X
Hematology* [;] ^{\$}	X	X	X	X	X	X
Biochemistry** [;] ^{\$}	X	X	X	X	X	X
Chest X Ray/CT scan ##	X	X	X	X	X	
Randomisation	X					
Best Supportive Care		X	X	X	X	
Pre-medication @ in Arm A		X	X	X	X	
ALZUMAb infusion ^b		X	X	X	X	
Cytokines and Immunophenotyping assessment	X	X ^d				
PaO ₂ /FiO ₂ ratio	X	X	X	X	X	
CRP	X	X	X	X	X	X
Daily Morning SOFA Score ^c	X	X	X	X	X	
Concomitant medication check	X	X	X	X	X	X
Adverse events	X	X	X	X	X	X

[^] Window period: ± 48 Hours.

^a All inclusion / Exclusion criteria to be reviewed prior to first dosing. Screening period is up to 14 days however screening and baseline visit can happen in one day and screening assessment can be considered as baseline assessments.

^b 1.6 mg/kg dose iv infusion, if well tolerated and improvement in patient observed, investigator has the discretion to continue with 1.6 mg/kg dose every 2 weeks or 0.8 mg/kg weekly regimen in combination therapy with standard of care (anti-viral and antibiotic drugs). Subsequent dose and frequency can be modified, deferred or stopped if patient recovers as per investigator's

discretion. If patients' overall parameters improve (if performed and RT-PCR is negative) further dose need not be given. Total infusion received during study duration can vary from 1 to 4 for each patient. If patient recovers/is discharged earlier than 30 days, then patient should be contacted telephonically to get status of the patient on 30th day after enrolment.

c: Daily SOFA Scoring until patient moved out of ICU/equivalent, and later SOFA score frequency as per investigator discretion. If patient is not admitted in the ICU/equivalent at the time of enrolment, then it is recommended to capture these assessments daily for first 7 days.

Window period for assessment at 4th week or 30th day is \pm 3 days.

*Hematology assessments (blood test) include: hemoglobin, total leukocyte count, differential count, absolute neutrophil count, absolute lymphocyte count, and platelet count.

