## **6 General Aspects for Statistical Methods**

In general, metric variables and derived parameters will be presented using descriptive summary statistics including arithmetic mean, standard deviation, median, minimum and maximum.

Categorical variables will be presented using descriptive summary statistics including number of patients and percentages. Percentages of patients will be based on non-missing values. The presentation will be by treatment group. Individual values as well as minimum and maximum will be presented with the same number of decimal places as the raw data. Derived parameter will have as many decimal places as the measured number with the smallest number of decimal places. Descriptive statistics, such as arithmetic/geometric mean and median will be presented with an additional decimal place and standard deviation with two additional decimal places as the raw or derived data. All relevant subject data will be included in the listings; and all subjects entered into the database will be included in subject data listings. SAS 9.4 or any other validated software will be used for analysis purpose and generating Tables, Listings & Figures. P-values less than 0.05 may be reported as statistically significant.

The formatting of the final version of a table, figure, or listing may differ from what is presented in the mock shell or the presentation of the results may be changed, however the key content will remain unchanged. Additional tables, figures, and listings may be generated to supplement the planned output.

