## 14.1.2 Disposition of Patients

Disposition	Arm A [n (%)]	Arm B [n (%)]
Randomized	XX (XX.X %)	XX (XX.X %)
ITT/FAS Population	XX (XX.X %)	XX (XX.X %)
Safety Population	XX (XX.X %)	XX (XX.X %)
Completed the study	XX (XX.X %)	XX (XX.X %)
Completed 30 days follow up in hospital		
Early discharged*		
Discontinued	XX (XX.X %)	XX (XX.X %)
Reasons for Discontinuation		
Adverse event	XX (XX.X %)	XX (XX.X %)
Death	XX (XX.X %)	XX (XX.X %)
Physician decision	XX (XX.X %)	XX (XX.X %)
As per Protocol	XX (XX.X %)	XX (XX.X %)
Lost to follow up	XX (XX.X %)	XX (XX.X %)
Subject/Guardian decision	XX (XX.X %)	XX (XX.X %)
Diagnosis of COVID 19 by RT-PCR		
Positive	XX (XX.X %)	XX (XX.X %)
Negative	XX (XX.X %)	XX (XX.X %)
Not Available	XX (XX.X %)	XX (XX.X %)

\* Patients discharged early due to clinical improvement and government policy during the study.

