### 14.2.3 Reduction in proportion of patients who need Non-invasive ventilation

Visit		Arm A (N=XX)	Arm B (N=XX)
	Patients on Non-invasive ventilation at baseline	XX	XX
Day 7	N	XX	XX
	Stable or improved (shifted to bag and mask, NRBM, FM, nasal canula or off O2)	XX (XX.X %)	XX (XX.X %)
Day 14	N	XX	XX
	Stable or improved (shifted to bag and mask, NRBM, FM, nasal canula or off O2)	XX (XX.X %)	XX (XX.X %)
Day 21	N	XX	XX
	Stable or improved (shifted to bag and mask, NRBM, FM, nasal canula or off O2)	XX (XX.X %)	XX (XX.X %)
Day 30/EOS	N	XX	XX
	Stable or improved (shifted to bag and mask, NRBM, FM, nasal canula or off O2)	XX (XX.X %)	XX (XX.X %)

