### 14.2.11 Ordinal Scale: No and Proportion of patient reduced by 1 or more points

		Day 7 n (%)	Day 14 n (%)	Day 21 n (%)	Day 30/EOS n (%)
Arm A (n=XX)					
Arm B (n=XX)					

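### The discharge and death rules are stated only for primary endpoint 1; the other by-visit oxygen and severity tables default to non-missing values, which can attenuate or reverse a treatment effect

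*SAP*

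**What the plan says.** SAP 13 introduces its rules broadly and optionally: "Following Rules may be applied for the derivation of efficacy endpoints". For early discharge the rule is "Patients who discharged from hospital (with improvement, Off O2), the status at discharge will be carried forward". Patients who worsen or die keep their status at the event, patients lost to follow-up are non-evaluable, and weaning from oxygen reported by telephone counts as improvement. The section then closes with "These rules will be applied to analyse following endpoint" and lists only the stable SpO2 and stable PaO2 proportions, which are primary endpoint 1.

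For everything else there are two defaults:

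- SAP 6: "Percentages of patients will be based on non-missing values".
- SAP 12: a missing assessment may be taken from the following two days, or from two days either side for laboratory values.

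Early discharge is expected. The footnote to SAP 14.1.2 reads "Patients discharged early due to clinical improvement and government policy during the study". The contact that protocol 8.1, footnote b, provides after it is: "If patient recovers/is discharged earlier than 30 days, then patient should be contacted telephonically to get status of the patient on 30th day".

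The shells affected are:

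- **14.2.3 to 14.2.6** (NIV, NRBM, face mask, high-flow oxygen). Each gives the baseline users of the device and then a separate N at Days 7, 14, 21 and 30. The NIV row is "Stable or improved (shifted to bag and mask, NRBM, FM, nasal canula or off O2". The NIV and high-flow tables report part of primary endpoint 3.
- **14.2.10 to 14.2.12** (oxygen requirement and SOFA, ordinal scale, respiratory rate).
- **S1 to S6** (lymphocytes, P/F, PaO2, FiO2, SpO2; S3 covers Arm A only, by dose). S4 to S6 have no row for n.

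P/F ratio is secondary endpoint 3, and SAP 9 plans a 95% CI for its difference between treatments.

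**The concern.** A two-day window cannot fill the weeks after a discharge or a death, and one call at Day 30 cannot supply a Day 14 or Day 21 P/F ratio, SOFA score or respiratory rate. Under the stated default, the best outcomes (home, off oxygen) and the worst (dead) both tend to leave the later visits. What is left compares those still ill in each arm, not the groups being studied. If itolizumab does what the protocol hypothesises and reduces morbidity and mortality, discharge and death will differ by arm, and that is the setting in which the remaining comparison is most distorted.

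The device tables count coming off oxygen as improvement, so discharged patients look as if they were meant to be included. No rule puts them there.

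**Working it through.** There is no figure in the plan to reproduce. The sample of about 30 is stated without a calculation, and the documents give no discharge, death or P/F rates. All rates and counts below are assumptions, chosen to show what the open choice can do.

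**1. Arm sizes.** SAP 4.5 gives about 30 patients at 2:1, so 30 × 2/3 = 20 in Arm A and 30 × 1/3 = 10 in Arm B.

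**2. Assumed state at a later visit**

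| | Discharged off O2 (D) | In hospital, stable or improved (S) | In hospital, worse (W) | Died (X) | Total |
|---|---|---|---|---|---|
| Arm A | 12 | 3 | 3 | 2 | 20 |
| Arm B | 2 | 4 | 1 | 3 | 10 |

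The whole arm is used here. A single device table would have fewer patients.

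**3. Same patients, four denominators**

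| Handling | Formula | Arm A | Arm B | A minus B |
|---|---|---|---|---|
| All patients, discharge off O2 = improved, death = failure | (D+S)/(D+S+W+X) | 15/20 = 75% | 6/10 = 60% | +15 points |
| Still in hospital only | S/(S+W) | 3/6 = 50% | 4/5 = 80% | −30 points |
| Discharges kept, deaths dropped | (D+S)/(D+S+W) | 15/18 = 83% | 6/7 = 86% | −2 points |
| Fixed denominator, absent = not improved | S/(D+S+W+X) | 3/20 = 15% | 4/10 = 40% | −25 points |

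**4. The existing death rule does not settle it.** SAP 13 carries forward the status at the event. Someone who died on NIV could then count as stable. If every death were carried as stable, the result is (D+S+X)/total: 17/20 = 85% in Arm A and 9/10 = 90% in Arm B. Depending on status at death, Arm A lies between 75% and 85% and Arm B between 60% and 90%. The 75% versus 60% result needs death to be defined as failure.

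**5. How often the sign changes.** Simulated trials of 20 versus 10; reversal means Arm A is worse among patients in hospital, given that it is better among all patients.

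| Discharged, A vs B | Died, A vs B | Expected, all patients | Expected, in hospital | Reversed |
|---|---|---|---|---|
| 60% vs 20% | 10% vs 30% | 75% vs 60% | 50% vs 80% | 77% |
| 60% vs 40% | 5% vs 25% | 80% vs 60% | 20/35 = 57% in both | 40% |
| 50% vs 40% | 10% vs 20% | 75% vs 65% | 25/40 = 62.5% in both | 32% |

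The first row is a systematic reversal. In the other two the expected benefit among inpatients is zero, so the reversals there are chance variation around a benefit that has disappeared.

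**6. Measured values.** Assume P/F has mean 200 and SD 90 and is observed only between 90 and 300. A uniform true gain of 30 shrinks to 11.4 on average, and one of 60 to 21.6. The sign flips in 25% and 18% of the trials where Arm A is better overall. If only half the patients respond, the same average gains shrink to 9.8 and 13.7, with flips in 27% to 28%. If instead the drug keeps would-be deaths alive in hospital and speeds discharge of the better patients, the full difference is +7 to +10 while the in-hospital difference is −17 to −32, over three assumed P/F distributions.

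**The case against.** The strongest reply is that the SAP never limits these tables to inpatients. The lead-in, with 'may' and a plural, allows wider use of the rules. The device shells count off oxygen as improved. The shells for 14.2.11 and 14.2.12 show one n per arm and no N per visit. The telephone note could supply oxygen status at Day 30. Listings 16.1.12, 16.1.16 and 16.1.17 hold the oxygen-device, discharge and death dates, so device status at Day 14 can be derived for someone sent home off oxygen. The ordinal categories are not defined, so discharge and death may already have levels of their own.

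All of that stands against the reading that every other table is computed only on patients still in hospital. It does not supply a rule. An optional lead-in followed by a single named endpoint leaves the denominator to whoever programs the table, in an open-label trial that SAP 4.1 calls pivotal, and the choice can decide direction.

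It is also fair that SAP 9 mentions p-values only for primary endpoint 1 and mortality, that NRBM, face mask, ordinal scale, SOFA and respiratory rate are not listed endpoints, and that about 30 patients are exploratory. This limits the severity. It does not remove the point, because NIV and high-flow oxygen belong to a primary endpoint and P/F carries a between-arm CI.

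A reader might extend the concern to the intubation table, 14.2.2. That table is not by visit and loses nobody from its denominator, and deaths are reported by arm in 14.2.7. A composite of intubation or death would be a separate preference.

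**Conclusion.** The point holds as a should-fix. Discharge and death handling is written for primary endpoint 1 only. Elsewhere it is undefined, with a stated default to non-missing data that makes later visits depend on outcome.

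The usual effect of that default is attenuation. A reader might infer that reversal is to be expected, but neither the documents nor the calculations support this: under a uniform gain the average difference kept its sign, and systematic reversal needed marked differences in discharge or death between arms. A reader might also infer that applying the endpoint 1 rules everywhere would be enough. It would not, because carrying status at death forward can score a death on NIV as stable.

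The size shown (a 15-point lead becoming a 30-point deficit) rests on assumed counts, on death counted as failure, and on discharge off oxygen counted as improved. It shows what is possible and is not a forecast.

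**What to change.** In SAP 13, state for each table which patients are in the denominator and how discharge and death are classified, with 'will' in place of 'may'.

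For 14.2.3 to 14.2.6, 14.2.11 and 14.2.12:

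- The denominator at each visit is all baseline users of the device, or all ITT/FAS patients in the arm.
- Discharged off oxygen counts as improved.
- Discharged on oxygen is classified by the last recorded device status. This is needed because the 14.1.2 footnote also cites government policy as a reason for early discharge.
- Death counts as not stable or improved; status at the event is not carried forward.
- Lost to follow-up is shown as a separate non-evaluable count, in line with SAP 13.
- Status is derived from the dates in listings 16.1.12, 16.1.16 and 16.1.17.
- In 14.2.12, which uses rate bands, discharged and dead patients appear in rows of their own within the same denominator. In 14.2.11, say which scale levels they take.

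For 14.2.10 and S1 to S6, print n, died and discharged counts at each visit, and label the means as being among patients with a measurement. The between-arm CI for P/F should carry the same label. No change to 14.2.2 is needed.

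The cost is SAP wording, changed denominators and a few rows, with no new data; SAP 1 allows revision before database lock. The small downside is that discharge status is assumed to hold until the Day 30 call, which the SAP already assumes for primary endpoint 1.

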## Listing of Tables, Figures & Format

Table, figure, and listing shells are presented in Appendices 14. The formatting of the final version of a table, figure, or listing may differ from what is presented in the shell or the presentation of the results may be changed, however the key content will remain unchanged. Additional summaries/data points may be included in the final version of a table, figure, or listing, as well. Additional tables, figures, and listings may be generated to supplement the planned output.

### Software Detail

SAS version 9.4 or any validated statistical software will be used to generate all tables, figures and listings.

## 14 Tables and mock shells

### 14.1.1 Screening Failures

	Overall N (%)
Total Screened Subjects	XX (XX.X %)
Screen Failures	XX (XX.X %)
Total Randomized Subject	XX (XX.X %)
Subject met Inclusion Criteria or met Exclusion Criteria	XX (XX.X %)
Subject not met Inclusion Criteria or met Exclusion Criteria	XX (XX.X %)
Others	XX (XX.X %)

 
• Withdrawal Informed Consent
 
	XX (XX.X %)

 
• Lost to Follow-Up
 
	XX (XX.X %)
.....	

Note: XX patients could not complete first dosing hence replaced as per the protocol.

## 14.1.2 Disposition of Patients

Disposition	Arm A [n (%)]	Arm B [n (%)]
Randomized	XX (XX.X %)	XX (XX.X %)
ITT/FAS Population	XX (XX.X %)	XX (XX.X %)
Safety Population	XX (XX.X %)	XX (XX.X %)
Completed the study	XX (XX.X %)	XX (XX.X %)
Completed 30 days follow up in hospital		
Early discharged*		
Discontinued	XX (XX.X %)	XX (XX.X %)
Reasons for Discontinuation		
Adverse event	XX (XX.X %)	XX (XX.X %)
Death	XX (XX.X %)	XX (XX.X %)
Physician decision	XX (XX.X %)	XX (XX.X %)
As per Protocol	XX (XX.X %)	XX (XX.X %)
Lost to follow up	XX (XX.X %)	XX (XX.X %)
Subject/Guardian decision	XX (XX.X %)	XX (XX.X %)
Diagnosis of COVID 19 by RT-PCR		
Positive	XX (XX.X %)	XX (XX.X %)
Negative	XX (XX.X %)	XX (XX.X %)
Not Available	XX (XX.X %)	XX (XX.X %)

\* Patients discharged early due to clinical improvement and government policy during the study.

### 14.1.3 Subject Disposition by Centre

Center Number	Arm A [n (%)]	Arm B [n (%)]
1	XX (XX.X %)	XX (XX.X %)
2	XX (XX.X %)	XX (XX.X %)
3	XX (XX.X %)	XX (XX.X %)
4	XX (XX.X %)	XX (XX.X %)

### 14.1.4 Summary of Demographic Characteristics

	Arm A [n (%)]	Arm B [n (%)]
Age (years)		
N	XX	XX
Mean (SD)	XX.X (XX.XX)	XX.X (XX.XX)
Median	XX.X	XX.X
Min, Max	XX, XX	XX, XX
Sex, n (%)		
Male	XX (XX.X %)	XX (XX.X %)
Female	XX (XX.X %)	XX (XX.X %)
Race, n (%)		
Asian	XX (XX.X %)	XX (XX.X %)
Black	XX (XX.X %)	XX (XX.X %)
Ethnicity		
Hispanic	XX (XX.X %)	XX (XX.X %)
East Asian	XX (XX.X %)	XX (XX.X %)

### 14.1.5 Summary of Concomitant Medication by treatment group

	Arm A (N=XX) [n (%)]	Arm B (N=XX) [n (%)]
Any medication taken		
Yes	XX (XX.X %)	XX (XX.X %)
No	XX (XX.X %)	XX (XX.X %)
ATC		
XXXXX	XX (XX.X %)	XX (XX.X %)
XXXXX	XX (XX.X %)	XX (XX.X %)
Medication Name	XX (XX.X %)	XX (XX.X %)
XXXXXXXXXXXX	XX (XX.X %)	XX (XX.X %)
XXXXXXXXXXXX	XX (XX.X %)	XX (XX.X %)
XXXXXXXXXXXX	XX (XX.X %)	XX (XX.X %)
XXXXXXXXXXXX	XX (XX.X %)	XX (XX.X %)
XXXXXXXXXXXX	XX (XX.X %)	XX (XX.X %)
XXXXXXXXXXXX	XX (XX.X %)	XX (XX.X %)

### 14.1.6 Summary of Medical History

	Arm A (N=XX) [n (%)]	Arm B (N=XX) [n (%)]
Diagnosis of COVID 19 by RT-PCR Positive , n (%)	XX (XX.X %)	XX (XX.X %)
Duration of COVID-19 related symptoms at enrolment		
N	XX	XX
Mean (SD)	XX.X (XX.XX)	XX.X (XX.XX)
Median	XX.X	XX.X
Min, Max	XX, XX	XX, XX
Patients with co-morbidities		
Diabetes Mellitus	XX (XX.X %)	XX (XX.X %)
Hypertension	XX (XX.X %)	XX (XX.X %)
Others	XX (XX.X %)	XX (XX.X %)
XXXX	XX (XX.X %)	XX (XX.X %)
XXXX	XX (XX.X %)	XX (XX.X %)

### 14.1.7 Summary of Vital Parameters and change from Baseline

Variable	Visit	Arm A (N=XX) [n (%)]	Arm B (N=XX) [n (%)]
Weight (kg)	Baseline		
	N	XX	XX
	Mean (SD)	XX.X (XX.XX)	XX.X (XX.XX)
	Median	XX.X	XX.X
	Min, Max	XX, XX	XX, XX
	48 hours		
	N	XX	XX
	Mean (SD)	XX.X (XX.XX)	XX.X (XX.XX)
	Median	XX.X	XX.X
	Min, Max	XX, XX	XX, XX
	Change from Baseline		
	N	XX	XX
	Mean (SD)	XX.X (XX.XX)	XX.X (XX.XX)
	Median	XX.X	XX.X
	Min, Max	XX, XX	XX, XX

Note: \*: repeated for Weight, Body Temperature, Pulse, Systolic, Diastolic, Respiratory Rate, PaO2/FiO2, FiO2, SpO2, Mean Arterial Pressure, Glasgow Coma Scale, PaO2 etc

# Repeated for Day 7, Day 14, Day 21, Day 30 and EOS

### 14.1.8 Summary of Laboratory Test Results and Change from Baseline: Hematology

Test	Visit	Arm A (N=XX) [n (%)]	Arm B (N=XX) [n (%)]
Haematocrit* %	Baseline&		
	N	XX	XX
	Mean (SD)	XX.X (XX.XX)	XX.X (XX.XX)
	Median	XX.X	XX.X
	Min, Max	XX, XX	XX, XX
	Day 7		
	N	XX	XX
	Mean (SD)	XX.X (XX.XX)	XX.X (XX.XX)
	Median	XX.X	XX.X
	Min, Max	XX, XX	XX, XX
	Change from Baseline&&		
	N	XX	XX
	Mean (SD)	XX.X (XX.XX)	XX.X (XX.XX)
	Median	XX.X	XX.X
	Min, Max	XX, XX	XX, XX

&: Repeat for day 14, Day 21, 30/EOS for all applicable parameters,

&&: Repeat for Day 14, Day 21, Day 30/EOS Change from Baseline

\*: Haemoglobin, Total leukocyte count, Platelet count, Absolute lymphocyte count, Absolute neutrophil count, Basophils- Differential, Eosinophils- Differential, Lymphocytes- Differential, Monocytes- Differential and Neutrophils- Differential.etc

### 14.1.9 Summary of Laboratory Test Results and Change from Baseline: Biochemistry

Variable	Time point	Visit	Arm A (N=XX) [n (%)]	Arm B (N=XX) [n (%)]
Blood Urea*	Predose	Baseline &		
		N	XX	XX
		Mean (SD)	XX.X (XX.XX)	XX.X (XX.XX)
		Median	XX.X	XX.X
		Min, Max	XX, XX	XX, XX
		12-24 hours		
		N	XX	XX
		Mean (SD)	XX.X (XX.XX)	XX.X (XX.XX)
		Median	XX.X	XX.X
		Min, Max	XX, XX	XX, XX
		Change from Baseline		
		N	XX	XX
		Mean (SD)	XX.X (XX.XX)	XX.X (XX.XX)
		Median	XX.X	XX.X
		Min, Max	XX, XX	XX, XX
	12-24Hrs Post Dose	Day 7 &&		
		N	XX	XX
		Mean (SD)	XX.X (XX.XX)	XX.X (XX.XX)
		Median	XX.X	XX.X
		Min, Max	XX, XX	XX, XX

&: Repeat for day 14, Day 21, 30/EOS for all applicable parameters , Change from Baseline, Week 3, Change from Baseline, Week 4 and Change from Baseline

&&: Repeat for Day 14, Day 21, Day30/EOS 2, Change from Baseline,

\*: Serum Bilirubin, AST (SGOT), ALT (SGPT), ALP, Serum Albumin, LDH, HDL, LDL, Triglycerides, Total Cholesterol, Serum creatinine, Procalcitonin, d-Dimer, Trop-I, Ferritin etc.

### 14.1.10 Hospitalization

	Arm A (N=XX) [n (%)]	Arm B (N=XX) [n (%)]
Was patient hospitalized during study?		
Yes	XX (XX.X %)	XX (XX.X %)
No	XX (XX.X %)	XX (XX.X %)
Discharged During study		
Yes	XX (XX.X %)	XX (XX.X %)
No	XX (XX.X %)	XX (XX.X %)
N/A	XX (XX.X %)	XX (XX.X %)
Was patient in Intensive Care Unit during this hospitalization period		
Yes	XX (XX.X %)	XX (XX.X %)
No	XX (XX.X %)	XX (XX.X %)

